Although the preliminary results of the new Thulium laser look promising, there are no clinical randomized trials comparing it to the Holmium laser, which is the current standard laser used for URS lithotripsy.

Aims of the study:

The primary aim of the study is to compare the stone free rate (SFR) following URS lithotripsy with Holmium and Thulium lasers. SFRs will be compared both for ureteral stones, renal stones and ureteral and renal stones in total.

Secondary aims are to compare the results of the two lasers in terms of operating times, intraoperative complications, postoperative complications and the rate of post endoscopic JJ-stenting.

Hypothesis:

1. The SFR, defined as no residual fragments detected on CT scan 3 months after the URS, is higher following lithotripsy with Thulium laser compared to Holmium laser. The corresponding H_0 is that "*there is no difference in SFR following laser lithotripsy with the two lasers.*"
2. Operating time following Thulium laser lithotripsy is shorter compared to Holmium laser. H_0 : "*There is no difference in the operating time between the two laser machines.*"
3. There are less intraoperative complications during Thulium laser lithotripsy compared to Holmium laser. H_0 : "*There is no difference in intraoperative complications between the two laser machines.*"
4. There are less postoperative complications (infections, readmissions, strictures) during Thulium laser lithotripsy compared to Holmium laser. H_0 : "*There is no difference in postoperative complications between the two laser machines.*"
5. Fewer patients will need post endoscopic insertion of JJ-stent following Thulium laser lithotripsy compared to following Holmium laser lithotripsy. The corresponding H_0 is that "*there is no difference in the frequency of post endoscopic JJ-stent placement following laser lithotripsy with the two lasers.*"

Study design:

The study is planned performed as a prospective randomized trial. All patients ≥ 18 years scheduled to URS lithotripsy at the day surgery unit at HUH are invited to be enrolled in the study. After written informed consent, patients are randomized to URS lithotripsy with either Holmium laser or Thulium laser.

Randomization:

The randomization is performed electronically with the same number of patients in each group. The results of the randomization are being kept in sealed and consecutively numbered envelopes that is opened just before starting the endoscopic procedures in each patient.

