Patients and data sampling:

All patients ≥ 18 years scheduled for URS lithotripsy at the day surgery unit at HUH are basically eligible for inclusion in this study. Patients with either ureteral stones, renal stones or both can be included. The number of patients/procedures needed to be included in the study is specified in the Power analysis-section below.

The following data need to be registered:

- *Preoperative status:* Age, sex, ASA-status, indication for surgery, earlier surgery for same stone, stone status, acute/planned surgery, prestenting-status, infection.
- *Peroperative characteristics:* Randomization status, primary surgeon, antibiotic prophylaxis, operating time, need for safety guide wire and access sheath, type of endoscope (semi-rigid/flexible), balloon dilatation, impacted stone, successful access to the stone, laser modality, laser settings, laser time and energy used, dusting or fragmentation, retrieval of fragments or left for spontaneous passage, surgeon's assessment of post

- endoscopic stone free status, complications, placement of JJ-stent.
- *Postoperative status:* Length of hospital stay, immediate complications that need urgent treatment, complications after discharge requiring readmission, 3-months follow-up with CT scan (SFR, stricture rate).

The data will be plotted in a registration form which will be available both electronically and on paper. If paper form is used, the data will be registered electronically subsequently and the paper-form maculated. Completed registration-forms are transferred to a SPSS database for statistical analyses.

The registration-forms and the database will be stored at Helse-Bergen's scientific and research server in a designated file assigned from the Data Protection Officer. An ID-Key file combining personal ID to the registration form will be stored at a designated server for this purpose at Helse-Bergen's research servers. Only the project manager ([name]) will have access to this ID-Key file.

The registration forms and the ID-Key file will be kept on the server for five years after the study has been completed in accordance with the law. After five years the data will be made anonymous in terms of deleting the ID-Key file.

Power analysis:

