In an earlier study, we found the 3-months SFR after Holmium laser URS lithotripsy to be 54.2% using a strict definition of *no* residual fragments detected on CT scan³. Although this is a strict definition, it leaves no room for personal judgement whether a patient is stone free or not. The definition is therefore suitable for this study purpose.

We expect the Thulium laser to be more efficient in clearing stones than the Holmium laser, with a total SFR of around 80% after URS lithotripsy using this laser.

Comparison of the SFRs between Holmium and Thulium laser will be done using the χ^2 -test. An effect size of 0.3 is considered appropriate assuming the SFRs after Holmium and Thulium laser lithotripsy to be 54.2% and 80%, respectively. The α error probability is set to 0.05 and the power (1- β error probability) is set to 0.8. Comparison of the SFRs following URS with the

two lasers with χ^2 -test is based on a 2 x 2 table, and in this case with only 1 degree of freedom (Df).

Using G*Power, version 3.1.9.4 for power analysis, the total sample size is calculated to be 88. To compensate for possible non-evaluable patients, a total of 120, i.e. 60 patients in each group, are planned to be included in the study.

Statistical analyses:

Statistical analyses will be performed using IBM SPSS Statistics 25 or higher (IBM, Armonk, NY). A p -value < 0.05 will determine statistical significance.

Continuous variables will be compared using independent-samples t -tests, or in the cases where a normal distribution is not met, Mann-Whitney U test. Exact chi-squared test and Fisher's Exact test are used comparing categorical variables.

Ethical considerations, ethical approval and patient consent

Holmium laser lithotripsy is the gold standard during URS today and is in use worldwide. Preliminary results with the new Thulium laser seem promising, however, no randomized trials comparing the outcome of the two laser modalities exists. The planned study therefore seems to be highly clinically relevant. In addition, the new Thulium laser is approved for use during endoscopic lithotripsy and the patients should therefore not be exposed to extra risk of harm using this laser.

Applications for approval by The National Committees for Research Ethics in Norway and The Data Protection Authorities at HUH will be sent prior to study start. In addition, the study will be registered in the clinical research database for randomized trials, ClinicalTrials.gov.

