All patients eligible for inclusion in the study will receive oral and written information. Participation in the study is voluntarily, and the patient can choose to withdraw at any point during the study process. Inclusion in the study will only be done after the consent form is signed. The patient information and consent form used for this purpose is obtained from The National Committees for Research Ethics in Norway's website (https://helseforskning.etikkom.no/frister/malforinformasjonsskriv?p_dim=34672).

Laser settings

The laser settings in the two study groups need to be standardized. The following laser settings are suggested as the start-up settings. In the cases of insufficient effect, higher energies can be applied but then need to be registered.

Ureteral stones: 0.4 J at 6 Hz (2.4 watts), long pulse

Renal stones: 0.4 - 0.8 J at 6 - 20 Hz (2.4 - 16 watts) for Holmium and
0.6 - 0.8 J at 30 Hz (18 - 24 watts) for Thulium.

The initial settings for the Thulium laser when treating renal stones are at a higher watt-level compared to the Holmium laser settings, and is therefore expected to be more efficient. However, the fact that the Thulium laser is able to deliver more energy needs to be considered when comparing the clinical outcome of the two lasers.

Study progress

The date for completing the data registration form, patient information and consent form, and application for approval by The National Committees for Research Ethics in Norway is set to 18th of August 2020.

During August 2020 the application form to The Data Protection Authorities at HUH will be sent. Prior to study start the study will also be registered in the clinical research database for randomized trials, ClinicalTrials.gov.

Inclusion of patients and ureteroscopies is expected to start in October 2020, and the inclusion is expected to close during March 2021.

Data analyses and writing a draft is set to spring 2021. Final manuscript ready for submission is planned during the summer 2021.

Funding

No external funding is planned. Hopefully, the project can be completed during regular working hours at Haukeland University Hospital and the University of Bergen.

Conflicts of interest

[name] is a consultant for Olympus, who was not involved in the design, collection, analyses, interpretation or reporting of the data. The two other authors have nothing to disclose.

Publication of data

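### Does setting the analysis for spring 2021 mean the stone-free rate is compared before the last 3-month CT is in?

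*Combined protocol and SAP*

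**What the plan says.** Hypothesis 1 in the protocol defines the primary outcome as "no residual fragments detected on CT scan 3 months after the URS". The list of data to be registered, under Patients and data sampling, repeats the 3-month CT as a postoperative item.

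Study progress gives three dates:

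- Accrual: "Inclusion of patients and ureteroscopies is expected to start in October 2020, and the inclusion is expected to close during March 2021".
- Analysis: "Data analyses and writing a draft is set to spring 2021".
- Manuscript: "Final manuscript ready for submission is planned during the summer 2021".

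The Power analysis section asks for 88 patients and plans "a total of 120, i.e. 60 patients in each group", the surplus being meant to cover non-evaluable patients. The Statistical analyses section sets significance at p < 0.05. Nowhere does the protocol give a data cut-off, a database lock, a window for the CT, an interim analysis, or a statement that the analysis waits for the last scan.

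**The concern.** Three months after March is June, and on the usual March-to-May reading of spring every patient treated in March is scanned after the analysis period has ended. If the schedule were followed to the letter, one of two things could happen. The SFR comparison might be run once without the latest patients, at a cost in power. Or it might be run in spring at the 0.05 level and again on the full 120 with no adjustment, which would raise the type I error. Investigators who had seen results by arm might also pursue the outstanding CTs less evenly. With no lock date or waiting rule, nothing in the text expressly rules these out.

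**Working it through.** **The plan's own sample size.** For a chi-square test with 1 df, w = 0.3, α = 0.05 and noncentrality N·w², the smallest N with power of at least 0.80 is 88 (power 0.804; N = 87 gives 0.799). The stated 88 reproduces.

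**When the last CTs fall due (surgery date plus 3 calendar months).**

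| Surgery | CT due |
|---|---|
| 28 February 2021 | 28 May 2021 |
| 1 March 2021 | 1 June 2021 |
| 15 March 2021 | 15 June 2021 |
| 20 March 2021 | 20 June 2021 |
| 31 March 2021 | 30 June 2021 |

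**How many would be outstanding at the end of spring.** Assumption: 120 patients accrue uniformly from 1 October 2020 to the closing date. Complete = 120 × (days of accrual at least 3 months before the cut) / (total days of accrual). For closure on 31 March and a cut on 31 May this is 120 × 151/182 = 99.6. The protocol defines neither the end of spring nor the day in March, so both are varied.

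| Inclusion closes | Spring ends | Complete | Outstanding |
|---|---|---|---|
| 1 March | 31 May | 120 × 151/152 = 119.2 | 0.8 |
| 15 March | 31 May | 120 × 151/166 = 109.2 | 10.8 |
| 31 March | 31 May | 120 × 151/182 = 99.6 | 20.4 |
| 31 March | 20 June | 120 × 171/182 = 112.7 | 7.3 |
| 20 March or earlier | 20 June | 120 | 0 |

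**Power in the worst of these cases.** Round down to 99 patients.

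- At the protocol's w = 0.3, power is 85% (91% at 120).
- From the protocol's own rates, w = √[(0.542 − 0.80)² / 4 / (0.671 × 0.329)] = 0.2746. Power is then 78% at 99 and 85% at 120. On this w the 80% target needs 105 patients.

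**Cuts earlier in spring.** With closure on 31 March, about 61 patients would be complete at 31 March and 81 at 30 April (power 57% and 70% at w = 0.2746). Both are below 88. They apply only if SFR is compared at, or a month after, the close of recruitment, which the protocol does not say.

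**Type I error with two looks.** Testing at 0.05 on n patients and again on 120, using a bivariate normal with correlation √(n/120), gives 8.3%, 7.6% and 7.0% for n = 61, 82 and 99. The arithmetic is right, but it describes a procedure that appears nowhere in the plan. One comparison is specified, and one comparison spends 5%.

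**What can be done in spring.** Operating time, intraoperative complications and post-endoscopic stenting are all recorded at surgery. They are complete for all 120 when recruitment closes. Analysis work and drafting can start then without touching SFR.

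**The case for a change.** The strongest case for a change is that the protocol is silent where one sentence would do. Investigators are not blinded (the envelope is opened just before the procedure), and no text stops them comparing arms while CTs are outstanding. Starting the analysis in spring and finishing in summer could in practice mean two looks at SFR. The 32 places above 88 were meant for real losses, and a cut at 31 May would use up to 21 of them before anyone is lost. Against the 105 implied by the stated rates, 99 is already short.

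Part of this stands. The dates do not fit exactly, the silence is genuine, and a very early cut would be underpowered. But the shortfall against 105 comes from rounding the effect size up to 0.3, which is a separate matter from the calendar. The second look has to be read into the plan. Uneven pursuit of late CTs is a possibility rather than a shown bias: the scan is a listed item for every patient, and surgeons know the arm from the day of surgery whether or not anyone analyses early.

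**Conclusion.** This is a loose timeline, not a flaw in the analysis. The accrual dates are labelled as expectations and the manuscript date as planned; none is an analysis rule. The endpoint definition already settles the order of events, because a patient has no SFR result until the 3-month CT exists. All CTs fall due by 30 June 2021 if inclusion closes on 31 March, which still allows a manuscript in summer.

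Even a literal cut at 31 May would leave out only the most recent entrants in both randomised arms. The comparison would stay unbiased, with about 99 patients against the stated 88. The gap is between 0 and about 20 patients (at most 17% of 120), and power at the worst end-of-spring case is 78% to 85%, depending on which effect size is used.

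These sizes rest on uniform accrual, on recruitment closing within March as forecast, and on spring ending between 31 May and about 20 June. Writing down a lock date would tidy the document but would not alter the trial's conclusion, so no change is called for.
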